7.2. Protocol Deviations

A summary of subject-specific protocol deviations will be provided by treatment and actual baseline ordinal score ([Table 11](#)). Summaries will include the reason for the deviation and the deviation category for all subjects. All subject-specific protocol deviations and non-subject specific protocol deviations will be included in listings ([Listing 3](#) and [Listing 4](#)).

7.3. Investigational Product Exposure and Compliance

The number of subjects with halted, slowed, or missed investigational doses will be summarized for the investigational product by treatment and actual baseline ordinal score ([Table 12](#)).

For subjects with doses missed, halted or slowed, a listing of treatment exposure will be provided by subject number, treatment start/end dates, treatment duration in days, volume administered, and the number of missed, halted or slowed doses as well as the corresponding reasons ([Listing 10](#)). Total duration of exposure will be defined as last dosing date of investigational product – first dosing date of investigational product + 1, regardless of any temporary interruptions in study product administration, and will be expressed in days using up to 1 decimal place (e.g., 5.5 days).

8. EFFICACY EVALUATION

All efficacy analyses will be summarized and performed on the mITT and/or ITT populations by treatment and baseline ordinal score. Each stage will be summarized and listed separately. If the handling of any subject's primary or key secondary endpoint data is unclear, the subject's data may be reviewed by a blinded endpoint review committee (ERC), see Section 6.5 for more details on the ERC.

8.1. Primary Efficacy Analysis

Analysis of the primary endpoint, clinical status (8-point ordinal scale) on Study Visit (not necessarily actual) Study Day 8, will be analyzed using a proportional odds model with baseline steroid use and baseline ordinal score as covariates (primary analysis of the primary endpoint) after multiple imputation. See Section 6.5 for details regarding handling of missing ordinal score data.

The null hypothesis for active treatment over control is:

$$H_0: OR = 1$$

and the alternative hypothesis is:

$$H_A: OR \neq 1$$

where:

OR = common odds ratio

The treatment odds ratio at Day 8 estimated from the model will be presented along with the corresponding 95% and 80% confidence intervals, and the p-value (Table 16). Subjects in the shared control arm can only be used in comparison of any given intervention 'A', if they were eligible for 'A' and consented to randomization to 'A'; thus controls randomized at clinics where 'A' is not currently being studied are not compared to subjects in the 'A' arm. Odds ratios between the binary progression strata from the proportional odds model are reported in Table 22 for mITT population and Table 23 for ITT population at Day 8.

Refer to Table 6 for a list of covariates and subgroup analyses for this endpoint. Refer to Table 7 for imputation methods to be applied to this endpoint.

Results of the sensitivity, supplemental and subgroup analyses for ordinal score at Day 8 are provided in Table 16. Adjusted odds ratios of inferior clinical status at Day 8 along with their 95% CIs and 80% CIs are presented overall and within each subgroup in Figure 2 and Figure 3. These analyses will be repeated for the ITT population and results will be in Table 19.

Individual listing of ordinal score and its components will be provided in Listing 13.

8.2. Secondary Efficacy Analyses

8.2.1. Key Secondary Efficacy Analyses

Recovery will be defined as having a value of 1, 2, or 3 on the clinical status 8-point ordinal scale. The time to sustained recovery will be defined as the elapsed time (in days) from Study Day 1 to the day prior to the earliest recorded day at which a subject reaches recovery or hospital discharge and doesn't worsen (ordinal score > 3) up to and including Study Day 60. For example, a hospitalized subject with an ordinal score of 3 on Study Day 7 and doesn't worsen up to and including Day 60 will have a time to sustained recovery of 6 days, since ordinal score is reflective of the prior 24-hours.

For the primary analysis of sustained recovery endpoint, any subjects whose last assessment in the study is prior to an observed recovery will be censored at the day of their last observed assessment. For the sensitivity analysis of this endpoint, subjects whose last assessment in the study is prior to an observed recovery before Day 57 (beginning of Day 60 window) and who were discharged to a location other than LTAC, hospice care, or other hospital will be considered recovered and censored at Day 60. For both primary and sensitivity analysis of this endpoint, subjects who complete follow-up but do not experience sustained recovery will be censored at the day of their Study Day 60. All deaths that occur on or before Study Visit Day 60 will be considered not recovered and censored at Day 60. Note that we do not expect many subjects to worsen after discharge.

If a subject's last assessment is before Day 57 and is discharged to a location other than hospice, another hospital, or long-term care facilities, the subject will be considered recovered at the time of discharge for the sensitivity analysis but may be reviewed by the Endpoint Review Committee, if other data suggests the subject may not be recovered (e.g., to a location other than a private residence or discharged on high flow oxygen). If a subject is discharged to hospice or another hospital, or is a special case where recovery handling may be unclear, the subject's data may be reviewed by the Endpoint Review Committee to make the determination of whether the subject should be considered to have sustained recovery and, if so, at what time point in the analyses. Subject data to be reviewed as part of this determination will include the reported clinical status scores while hospitalized, where the subject was discharged to (e.g., private residence, rehabilitation facility, long-term care/nursing home, comfort care), and any information regarding readmittance. Additional information may be solicited to assess recovery.

Refer to [Table 6](#) for a list of covariates and subgroup analyses for this endpoint. Refer to [Table 7](#) for imputation methods to be applied to this endpoint.

The main analysis of the first key secondary endpoint (time to sustained recovery up to and including Study Day 60) conducts a score test to compare treatment to control up to and including Study Day 60. The treatment median survival time, confidence intervals and p-value from the score test will be presented ([Table 28](#)). Restricted mean recovery time estimates will be provided for each treatment group and actual baseline ordinal score stratum as well as the difference in restricted mean recovery time between treatment groups within each of the baseline ordinal score strata ([Table 29](#)).

Kaplan-Meier curves for each treatment arm will be presented and supplemented with the hazard ratio estimate, p-value, and the number of subjects at risk in each treatment at Study Day (not necessarily actual Study Days 1, 3, 5, 8, 11, 15, 22, 29, and 60) ([Figure 8](#)).

If the key secondary endpoint is different than what is covered in this SAP, it will be highlighted for each individual stage in the corresponding stage-specific appendix along with the subsequent analysis.

Each subgroup from [Table 6](#) will be considered separately, and the tabular and graphical summaries described above will be replicated for each subgroup ([Table 20](#)). A forest plot will be generated to display 95% and 80% CIs for hazard ratios from each of the subgroup analyses ([Figure 16](#), [Figure 17](#)).

Proportion of Subjects Alive and Without Respiratory Failure up to and Including Study Day 29

Any subjects whose last assessment is prior to death or progression to respiratory failure and prior to Day 26 (beginning of Day 29 window) will be censored at the date of their last observed assessment. For the sensitivity analysis of this endpoint, subjects whose last assessment is prior to obtaining the event and who were discharged to a location other than LTAC, hospice care, or other hospital will be considered recovered and censored at Day 29. For both primary and sensitivity analysis of this endpoint, subjects who complete follow-up will be censored Day 29. Events that occur after Day 29 will be censored at Day 29.

Kaplan-Meier estimates for the proportion of subjects with baseline ordinal score 5 or 6, who are alive and without respiratory failure up to and including Study Day 29 will be presented by treatment along with 95% CI from Kaplan-Meier (Table 30). Odds ratios and a p-value from an adjusted logistic regression model adjusting for covariates [2] detailed in Table 6 will be presented in Table 30. Risk differences and corresponding CIs obtained through bootstrap will also be generated using the approach discussed in [2] and results will be reported in Table 30. This analysis will be referred to as the primary analysis for the survival without respiratory failure endpoint.

Refer to Table 6 for a list of covariates and subgroup analyses for this endpoint. Refer to Table 7 for imputation methods to be applied to this endpoint.

Results of the primary, sensitivity, and subgroup analyses for this endpoint are reported in Table 30.

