Analysis of time to event endpoints (i.e., sustained recovery, time to improvement, time to mechanical ventilation or death) will be based on observed ordinal score without imputation along with discharge and death information. Refer to Table 7 for additional details regarding censoring and handling of missing data for all endpoints. As handling of missing data might differ for different stages of this study, stage-specific SAPs will provide additional details if handling of missing data for an endpoint for that stage differ from what is in the master SAP.

Table 7: Imputation Method for Each Endpoint and Analysis Type

Endpoint	Analysis	Imputation Method
Primary Endpoint		
1. Ordinal Score at Day 8	Primary	
 • If a subject is discharged from the hospital to another location other than LTAC, hospice care or other hospital, has intermittent missing ordinal score and reported an ordinal score of 1 or 2 after the missing score then: 
 ○ Impute the intermittent missing ordinal score as 1 if the scores reported before and after the missing value are both 1 and no change in oxygen use or hospitalization status after discharge to a location other than hospice, long term acute care or other hospital. ○ Impute the intermittent missing ordinal score as 2 after discharge to a location other than hospice, long term acute care or other hospital if the subject doesn't fall into the category above and subject is not hospitalized at the time point. • LOCF will be used for remaining intermittent missingness of ordinal scores for the next planned assessment. • All missing scores after death will be assigned an ordinal score of 8.

Endpoint	Analysis	Imputation Method
		
 Subjects discharged from the hospital to a location other than LTAC, hospice care or other hospital at their last assessment will be assigned a score of 2 for all timepoints after last assessment. Multiple imputation will be used to impute missing ordinal scores after last assessment for subjects still hospitalized or discharged to hospice, other hospital, or long-term care facility at their last assessment. See Section 6.5.2 for more details.

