	Primary with Sensitivity Imputation 1	
 Use the complete data for ordinal score to derive sustained recovery. Subjects whose last assessment in the study is prior to Day 57 (beginning of Day 60 window) after discharge from the hospital to a location other than LTAC, hospice care or other hospital will be treated as recovered by Day 60. Their time to recovery will be the day of their first observed/imputed recovery score (i.e., 1, 2, 3) or the day of discharge, whichever comes first. Subjects whose last assessment in the study is prior to Day 57 (beginning of Day 60 window) without being discharged from the hospital to a location other than LTAC, Hospice care or other hospital at their last assessment will be considered not recovered and censored at the date of their last assessment.

Endpoint	Analysis	Imputation Method
		
 Death prior to recovery will be considered not recovered and censored at expected study Day 60.
	Supplementary	
 Same imputation method as primary analysis for time to sustained recovery.
	Subgroup	
 Repeat analysis for each subgroup using same imputation as primary analysis for this endpoint.
2. Survival without respiratory failure up to and including Study Day 29	Primary	
 Subjects who complete follow-up without mechanical ventilation or death or who have the event after Day 29 will be considered non-events and censored at Day 29. Subjects whose last assessment in the study is before Day 26 (beginning of Day 29 window) and before experiencing death or progression to mechanical ventilation will be considered non-events and censored at the last assessment. Subjects whose last assessment in the study is before Day 29 but within window for Day 29 (i.e., Day 26, 27, 28) and before experiencing death or progression to mechanical ventilation will be considered non-events regardless of their discharge status and censored at Day 29.

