The time to mechanical ventilation or death up to and including Day 29 will be defined as the elapsed time (in days) from Study Day 1 to date of mechanical ventilation or death. Any subjects whose last assessment is prior to obtaining the event and prior to Day 26 (beginning of Day 29 window) will be censored at the date of their last observed assessment. For the sensitivity analysis of this endpoint, subjects whose last assessment is

prior to obtaining the event and who were discharged to a location other than LTAC, hospice care, or other hospital will be considered recovered and censored at Day 29. For both primary and sensitivity analysis of this endpoint, subjects who complete follow-up will be censored Day 29. Events that occur after Day 29 will be censored at Day 29. A table will present median time to event along with corresponding 95% and 80% confidence intervals for each treatment along with the hazard ratio estimate and score test p-value from a Cox-proportional hazard model (Table 42). The Cox model will include as covariates baseline ordinal score, baseline CRP value, continuous age, and baseline dexamethasone use. Differences in time-to-event endpoints by treatment will be summarized with Kaplan-Meier curves (Figure 11). Analyses will be performed on the mITT population for those subjects who at baseline have an ordinal score of 5 or 6, CRP<150 mg/L, and age<85 years and results will be reported in Table 42. This analysis will be repeated for all subjects in the mITT population and results will be reported in Table 43.

Refer to Table 6 for a list of covariates and subgroup analyses for this endpoint. Refer to Table 7 for imputation methods to be applied to this endpoint.

Hospitalization

Duration (in days) of hospitalization will be defined as the number of days subject is hospitalized for COVID-19-related reasons starting from the date of randomization. It will be calculated as the total number of days hospitalized, including readmissions for COVID-19-related reasons. It will also be calculated as the total number of days hospitalized, including any readmissions regardless of cause. See Section 6.5 for the plan for handling subjects who do not have data through Day 29 or die prior to Day 29.

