Female	Treatment A (N=X)	x	x.x	x.x	x.x, x.x	x.x, x.x	x.x	x.x, x.x	0.xxx
	Treatment B (N=X)	x	x.x	x.x	x.x, x.x	x.x, x.x			
	P-value for interaction ^e								0.xxx
CI=Confidence Intervals. N=Number of subjects in modified intent-to-treat (mITT) population. n= Number of unique recovered subjects that satisfies the row criteria. ^a Hazard Ratio (HR) is the hazard ratio calculated from the Cox Proportional Hazard Model comparing Active treatment vs Placebo. All subjects lost to follow-up before recovery are censored at last assessment date. ^b Primary with Sensitivity Imputation 1: Subjects discharged to a location other than LTAC, hospice care, or other hospital are considered recovered at Day 60. The rest of lost to follow-up subjects are censored at last assessment date. Model ^a was fit to estimate the HR, 95% CI and p-values. ^c Supplemental Analysis 1 (age and duration of symptoms prior to enrollment): In addition to the variable included in the model described in ^a , age and duration of symptoms prior to enrollment as additional covariates were added to the model when estimating the HR, 95% CI and p-values. Same censoring as in model ^a . ^d For the subgroup analyses, the model described in ^a was performed for each level of the subgroup. ^e P-value is based on the Cox adjusted model or P-value from interaction Type III test in subgroup analysis where the interaction between subgroup and treatment is being added to the Cox Proportional Hazard Model.									

Table 29: Time to Sustained Recovery through Day 60 by Treatment Group, Actual Baseline Ordinal Score, and Analysis Population: Restricted Mean Survival Time Analysis

Analysis Population	Treatment Group	Actual Baseline Ordinal Score	n	Tau ^a	Restricted Mean Recovery Time (Days)			Difference		
					Estimate	95% CI	80% CI	Estimate	95% CI	80% CI
mITT	Treatment A (N=X)	5	x	x	x.x	x.x, x.x	x.x, x.x	x.xx	x.xx, x.xx	x.xx, x.xx
	Treatment B (N=X)		x	x	x.x	x.x, x.x	x.x, x.x			
	Treatment A (N=X)	6	x	x	x.x	x.x, x.x	x.x, x.x	x.xx	x.xx, x.xx	x.xx, x.xx
	Treatment B (N=X)		x	x	x.x	x.x, x.x	x.x, x.x			
	Treatment A (N=X)	7	x	x	x.x	x.x, x.x	x.x, x.x	x.xx	x.xx, x.xx	x.xx, x.xx
	Treatment B (N=X)		x	x	x.x	x.x, x.x	x.x, x.x			
	Treatment A (N=X)	Any BOS	x	x	x.x	x.x, x.x	x.x, x.x	x.xx	x.xx, x.xx	x.xx, x.xx
	Treatment B (N=X)		x	x	x.x	x.x, x.x	x.x, x.x			
ITT	Treatment A (N=X)	5	x	x	x.x	x.x, x.x	x.x, x.x	x.xx	x.xx, x.xx	x.xx, x.xx
	Treatment B (N=X)		x	x	x.x	x.x, x.x	x.x, x.x			

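### SAP 8.2.1 makes good-discharge subjects last seen before Day 57 both recovered and censored in the sensitivity analysis of time to sustained recovery, against its own next paragraph and Table 7

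*SAP*

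**What the plan says.** Four places in the SAP describe the sensitivity analysis for a subject with a good discharge (not to LTAC, hospice or another hospital) who is last assessed before Day 57.

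- Section 8.2.1, first statement: those "discharged to a location other than LTAC, hospice care, or other hospital will be considered recovered and censored at Day 60". As written, it covers subjects whose last assessment precedes an observed recovery.
- Section 8.2.1, next paragraph: the subject "will be considered recovered at the time of discharge for the sensitivity analysis". This paragraph carries no such limit. The section then sends the reader to Table 7 for imputation.
- Table 7, Sensitivity Imputation 1: these subjects count as recoveries, dated as follows: "Their time to recovery will be the day of their first observed/imputed recovery score (i.e., 1, 2, 3) or the day of discharge". The earlier of the two is used.
- Table 28, footnote b: subjects discharged to a location other than LTAC, "hospice care, or other hospital are considered recovered at Day 60".

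Two further rules matter. Section 8.2.1 also says "All deaths that occur on or before Study Visit Day 60 will be considered not recovered and censored at Day 60". The censoring variable in Section 6.1 has two values, event observed or event not observed. The primary rule in Table 7 treats every subject last assessed before Day 57 as not recovered, censored at the last assessment.

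**The concern.** In a time-to-recovery analysis a recovered subject has had the event, and a censored subject has not. The first statement in 8.2.1 asks for both, and the planned coding has no value for that combination. A programmer who acts on the word censored gives a subject who went home well the time and status of a subject who died.

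The wording may have been carried over from neighbouring endpoints, though that is an inference. For survival without respiratory failure, 8.2.1 says subjects "discharged to a location other than LTAC, hospice care, or other hospital will be considered recovered and censored at Day 29", and 8.2.2 repeats "hospice care, or other hospital will be considered recovered and censored at Day 29" for time to ventilation or death. There the event is a bad outcome, so censoring a well subject is correct. Applied to recovery, the same phrase reverses the status.

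The sensitivity analysis is there to show how far the strict primary result depends on missed late contacts, by crediting good discharges as recoveries. With the status reversed it cannot do that.

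**Working it through.** The SAP gives no event count, power or effect size for this analysis, so there is no planned figure to reproduce.

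**Step 1: one subject under each text.** Take a subject with a last score of 4 on Day 10, discharged home that day, and no later contact. No recovery score was observed, so even the narrow scope of the first 8.2.1 statement applies. Section 8.2.1 counts to the day before the recovery day, so an event on Day 10 is 9 days.

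| Text | Record |
|---|---|
| 8.2.1, first statement, coded as censored | Day 60, no event |
| 8.2.1, rule for a death | Day 60, no event |
| 8.2.1, next paragraph | event, Day 10 (9 days) |
| Table 7, Sensitivity Imputation 1 | event, Day 10 (9 days) |
| Table 28 footnote b, read as a date | event, Day 60 |
| Table 7, primary | censored, Day 10 |

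The four sensitivity texts give three codings. Table 7 and the second paragraph of 8.2.1 separate only if a score of 3 precedes discharge. In SAP Table 4, category 3 is 1.2 of the 0.0 + 34.6 + 1.2 = 35.8 percentage points in categories 1 to 3 at Day 8. That is 1.2/35.8 = 3.4%, so the case is probably uncommon.

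**Step 2: size under stated assumptions.** None of these inputs is in the documents.

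- Control probability of not yet having recovered: S(t) = 0.15 + 0.85·exp(−0.09t). The active arm is S(t) raised to the hazard ratio (HR).
- A fraction m of recovered subjects has no contact from Day 57. Last contact is Day 29, or the recovery day if later.
- Lost subjects do not relapse.
- The censoring reading is applied to all lost recovered subjects, which is broader than the narrow scope.
- Cox model with Efron ties.

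Control recovery by Day 60 is 0.85 × (1 − exp(−5.4)) = 0.85 × 0.9955 = 84.6%. With m = 10%, 0.10 × 84.6 = 8.5 percentage points are lost.

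- Table 7 rule: 84.6%, median about 10 days.
- Footnote b as a date: 84.6%, of which 8.5 points fall on Day 60; median about 12 days.
- Censoring reading: 84.6 − 8.5 = 76.1%, median about 12 days.
- Strict primary: about 78%.

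Estimated HR when the true value is 1.30:

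| Loss, equal in both arms | Table 7 | Footnote b as date | Censoring reading | Strict primary |
|---|---|---|---|---|
| 5% | 1.30 | 1.28 | 1.26 | 1.27 |
| 10% | 1.30 | 1.27 | 1.24 | 1.25 |
| 20% | 1.30 | 1.25 | 1.20 | 1.22 |

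Other control curves at 10% loss, in the same column order: slower recovery (68% recover) 1.30 / 1.29 / 1.26 / 1.28; faster recovery (92% recover) 1.30 / 1.24 / 1.21 / 1.22.

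**Step 3: no true effect.** With equal loss every coding returns an HR of 1.00. With 5% loss on control and 15% on active, Table 7 gives 1.00, footnote b as a date about 0.89, the censoring reading 0.81 to 0.82, and the strict primary 0.83. The Table 7 coding would expose the artefact in the primary result. The censoring reading would appear to confirm it.

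**The case against.** The strongest reply is that the SAP largely settles this. The second paragraph of 8.2.1 fixes recovery at discharge for this analysis and points to Table 7, which is explicit. The Version 3.0 change summary (Section 15.3) describes the added analysis in the same terms. Footnote b is probably shorthand for status by Day 60, since read literally it would date every good discharge at Day 60. The first 8.2.1 statement also calls these subjects recovered and deaths not recovered, so it is not an instruction to treat them alike. Read narrowly, it does not reach a subject with scores of 1 or 2 recorded after discharge. Section 6.5.1 expects little missing data and plans chart review, and the Day 60 contact may be by telephone.

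Most of this stands, and it lowers the chance that the wrong coding is used. It does not remove the contradiction. No text says which rule prevails, and any subject covered by the first statement has already met the 8.2.1 definition, which counts hospital discharge. The narrow scope would make the effect smaller than in Step 2.

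A reader might also infer a second error from Section 6.5.1, where time-to-event analyses "will be based on observed ordinal score without imputation along with discharge and death information", while Table 7 calls for complete data. That section sends the reader to Table 7 for censoring and missing data. For sustained recovery, the Table 7 rule on subjects last seen before Day 57 most naturally governs. This is loose wording, not part of the error.

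**Conclusion.** The point holds as a self-contradictory rule in current SAP text, in conflict with the next paragraph of 8.2.1 and with Table 7. If coded as censoring for all such subjects, the sensitivity analysis would show less recovery than the strict primary (76.1% against about 78% of controls at 10% loss). It would also fail to reveal bias from unequal loss. The HR difference from the Table 7 coding is 0.04 to 0.10 for 5% to 20% equal loss at a true HR of 1.30 (1.30 − 1.26 and 1.30 − 1.20). These sizes rest wholly on the assumed curve and loss rates.

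Two stronger readings are tempting. One is that the SAP codes the subject in four incompatible ways. The texts support one clear outlier, one ambiguous footnote, and two rules that normally agree. The other is that the primary analysis is affected. The loosely worded primary text in 8.2.1 and Table 28 footnote a agrees in context with the strict Table 7 rule, so no primary conflict is shown.

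The effect is confined to a sensitivity analysis of a key secondary endpoint. A stage-specific SAP, not among the documents reviewed, could override the rule. It should be fixed before unblinding, so that no coding has to be chosen afterwards.

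**What to change.** 1. In the first sensitivity statement of 8.2.1, delete the clause that censors at Day 60. Apply the rule to any good-discharge subject last assessed before Day 57, whether or not a recovery score was observed. Set the event at the earlier of the first recovery score (1 to 3) and discharge, as in Table 7, converted to days by the day-prior convention of 8.2.1.
2. Give the second paragraph of 8.2.1 the same event time.
3. Reword Table 28 footnote b to say that subjects with a good discharge who are last assessed before Day 57 count as recovered by Day 60, with the event time as in Table 7.

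The primary rule stays as it is. Aligning Section 6.5.1 with Table 7 on observed versus complete data is optional tidying. The cost is a wording change and a check of the derivation program, with no new data and no new analysis.
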